4.4 Randomization

Randomization and enrolment will occur between six and 48 hours after delivery and the initial post-delivery blood loss. Postpartum women during this window (6-48 hours postpartum) will be screened, enrolled, and randomized to one of the two treatments groups. Individual randomization and allocation concealment will be done with the use of a web-based randomization software known as 'Sealed envelope' in a 1:1 ratio in blocks stratified according to study site (Table 1). Screening, consenting, enrolment and randomization will be done by dedicated and trained study research nurses/midwives at each participating study site.

4.5 Blinding

This study is a multicenter parallel, open label, superiority randomized controlled trial. It is impossible to blind the treatment allocation as the intervention is administered intravenously, and the control is administered orally. However, the primary outcome data will be objectively determined by laboratory evaluation and will be collected without bias. For the subjective secondary outcomes, using the Edinburgh Postpartum Depression Scale (EPDS), Quality of Life questionnaire, fatigue scale, Maternal Infant Bonding questionnaire and an adverse event form, the research nurse performing data collection for these outcomes will be blinded to group allocation. These patients' reported outcomes measures will be completed without knowledge of the group allocation except for data on treatment compliance. Data on treatment compliance will be collected only after all other outcome data for the individual's visit has been completed and submitted.

4.6 Study intervention

4.6.1 Administration of study drugs

Administration of ferric carboxymaltose (FCM): Eligible women randomized to the intervention arm (FCM) will be observed at the dedicated ward or daycare room for treatment initiation and will be given intravenous ferric carboxymaltose (FCM) in a single dose of 20mg/kg up to a maximum of 1000mg. This dose will be administered as an infusion diluted in 200 ml 0.9% sodium chloride and infused over a minimum of 15 - 20 minutes (Table 2). Thereafter, they will be observed closely for a minimum of 30 minutes after infusion. [Refer to IVON-PP Trial - Protocol for the administration of Intravenous Ferric

Carboxymaltose and the Emergency Treatment of Hypersensitivity Reaction Type 1 (Anaphylaxis); Protocol no 2].

Administration of Ferrous Sulphate (FS): The women randomized to the control arm (FS) will be given for take home, one **200mg tablet of study drug, ferrous sulphate** which contains 65mg of elemental iron, to be taken two times daily and 1 hour before meals or 2 hours after meals with a full glass of water till 6 weeks postpartum (Table 2). The study drug for the control arm (FS) will be prepared in sachets, dispensed, and packaged in 2-week, 4-week and 6-week doses for the appropriate visit schedule. The women will be sent daily reminders by text messages and asked to bring in their empty sachets for sighting and for a pill count and evaluation of compliance at each study visit.

Table 2: Oral and intravenous Iron dosing for intervention and control arms

Study arm	Study medications	Dose	Comments
Intervention	Drug: intravenous ferric carboxymaltose	Single dose of 20mg/kg (to a maximum of 1000mg)	A dose of 20mg/kg body weight (but not exceeding a max of 1,000mg) of ferric carboxymaltose will be given in 200mls of normal saline as a single dose infusion administered over 15 – 20 minutes
Control	Drug: oral ferrous sulphate	One 200mg tablet (65 mg elemental iron) 2 times daily	Treat with 2 times daily regimen till six weeks postpartum. ^{a, b}

a. All patients will also receive 5mg folic acid daily and 400mg Vitamin C daily.

In addition, all study participants in both arms of the study; FCM and FS will receive 5mg folic acid daily, Vitamin C 200mg two times daily unless in known cases of allergy or intolerance to vitamin c and/or folic acid and followed from enrollment till 6 months post-partum. They will be seen on the postnatal wards from six hours after delivery, and then followed up at the health facility or home at two, six and 12 weeks, and six months postpartum.

4.6.2 Malaria treatment and prevention

All participants will be screened at baseline (enrollment), two and six weeks postpartum for malaria parasitemia with SD BIOLINE Malaria Ag P.f and treated with artemisinin-based combination therapy or any other tolerated alternative if positive for malaria parasites.

4.7 Participant Identification

Each participant will be uniquely identified in the study by a combination of the study site code and a four-digit number to make a study ID number e.g., 01-0001, 01-0002 etc. The study site codes are pre-assigned

b. After six weeks, any women with Hb still less than 11g/dl will be treated with oral iron or further investigated for the cause of the anemia and treated appropriately.

and logged into the sealed envelope by the Chief Investigator as shown in **Table 1**. After signing the informed consent form, the patient will be assigned a Study ID automatically generated as she is randomized on the web-based randomization form.

[figure not shown]

Figure 2: Prospective (clinical trial) study design flowchart

4.8 Physical examination

Full physical examinations will be performed at baseline, and at each visit. Examination will include measurement of the patient's weight and blood pressure, body temperature. An abdominal palpation will be performed to ensure the uterus is well contracted in all women; a physical examination of the perineum will be performed at baseline to ensure any perineal trauma has been identified. A physical examination of the breasts/perineum/abdomen will be performed if clinically indicated during follow up visits.

Information about the physical examination must be entered into the patients' clinical case notes/files at the study sites. Significant findings such as abnormal swelling, skin lesions, signs of inflammation/infection that are present prior to receiving study medication must be included in the relevant medical history/current medical conditions in the source document and the electronic Case Report Forms (CRFs).

4.9 Laboratory evaluations

Standard clinical laboratory evaluations will be performed as follows:

- Hemoglobin concentration with the Hemocue haemoglobinometer at screening, two and six weeks and six months postpartum. Complete the *Hb check worksheet* as appropriate (*Appendix i*).
- Malaria rapid diagnostic test (RDT) with SD BIOLINE Malaria Ag P.f at enrollment, two and six weeks
 postpartum and if symptomatic for malaria at any time. Complete the *Malaria POCT worksheet* as
 appropriate (Appendix ii).
- Full blood count at baseline (enrollment), two weeks, six weeks, and six months postpartum. At each visit, 4mls of blood will be collected in an EDTA vacutainer. *Complete blood sample collection log for study visits on REDCap (Appendix iii)*.
- Iron profile: comprises serum iron, serum ferritin, serum transferrin and percentage transferrin saturation will be done at baseline (enrollment), six weeks and six months postpartum. At each visit, 4mls of blood will be collected into a Serum separating tubes (SST) tube. *Complete blood sample collection log for study visits on REDCap*
- Maternal serum phosphate and other biomarkers: The biomarkers of phosphate homeostasis and bone turnover to be measured are Vitamin D, alkaline phosphatase, total procollagen type 1 N-terminal propeptide (P1NP), fibroblast growth factor 23 (FGF23), calcium (Ca) and phosphate (PO4) at baseline (enrollment), 2 weeks (Ca, PO4 and ALP only) and at 6 weeks postpartum. Two (2) SST tubes will be used for sample collection and 4mls of blood will be collected in each tube.
 Complete blood sample collection log for study visits on REDCap.

All samples aside the point of care tests (POCT) will be analyzed at Synlab (an internationally accredited medical laboratory). As a third-party, a contract is in place between the University of Lagos and Synlab. The following steps will be taken at blood sampling:

- Research nurse assistants will collect blood sample as indicated for study visit using an appropriate vacutainer system.
- Complete the *laboratory tests request form* (Appendix iv) with participant's study ID, study site code and visit type (PP-1 to PP-4) to accompany the samples to the lab.
- Document date and time samples were taken and type of test in blood sample collection log on REDCap for study visit.
- Call the dispatch rider for samples pick up within 2-3 hours of sample collection.
- Store samples at 4-8°C (refrigeration) immediately after collection before pickup; for not more than 12 hours.

The result in CSV format will be entered into the e-CRF by the data management team as soon as received from the laboratory. Test results will be reviewed at the back end by the investigators and if any results

are of clinical concern, the site coordinator will be contacted to schedule a study visit, and a repeat sample will be collected at the earliest visit.

4.10 VISIT SCHEDULES AND ASSESSMENTS

Participants will be seen at the postnatal wards between 6 and 48 hours after delivery at study sites for enrolment then at two, six and 12 weeks postpartum and at the end of study (EOS) visit at six months postpartum. Aside the baseline visits for enrolment, all other visits will be done at the participants' home or at the healthcare facility depending on the participants' preference.

4.10.1 Screening & and consent (visit 0)

- The required information from this visit will be completed for all prospective participants in the *screening log* (Appendix v).
- All prospective participants are women who are within six and 48 hours after delivery.
- These women will be assessed using the study eligibility criteria (inclusion and exclusion)
- Those that meets the eligibility criteria will then have their hemoglobin concentration determined using the POCT haemoglobinometer. Complete the *Hb check worksheet* as appropriate.
- Participants with *Hb* ≤9.9g/dL who have been determined to meet other study eligibility criteria are then consented for participation in the study.
- Informed consent must be obtained at this visit when the prospective participant meets ALL study eligibility criteria.

The **informed consent process** is described below:

- The research nurse assistant will provide the full participant's information sheet to the prospective participant. Information will be disclosed to the prospective participant, and it will be ensured she comprehends the nature and purpose of the study, duration of participation, procedures to be done, community tracking as necessary including home visitations and laboratory investigations to be performed. She should also be made aware of any foreseeable risk and discomfort, other study requirements and visits schedule, participants' responsibility and be willing to freely participate.
- Acceptance/rejection to participate
- Agreement to participate (Consent) must be recorded (written) and witnessed where necessary. Each participant will be asked to sign (or provide other mark such as thump print if need be) *three copies* of an *informed consent document* (*Appendix vi*), in English or translated into Yoruba/Hausa/Igbo as appropriate. The participant will be given a signed copy to take home. If the participant cannot read, a witness must be present at the time of the information disclosure and consent process and will witness the signature or mark of the participant.

If a prospective participant is screened but does not get enrolled, the reason for not being enrolled must be documented in the screening log.

4.10.2 Enrollment and randomization visit (Visit 1)

Enrollment (visit-1) will preferably take place during the same visit/time as the screening (visit-0) or very shortly after within 6-48 hours after delivery.

• Once the participant has been screened and determined to meet study eligibility criteria and complete the informed consent document,

The following additional steps will be taken:

1. Go to Sealed Envelope and randomize the participant into a study arm.

- The participant will be assigned a study ID which will be used to identify the participant throughout the study.
- Complete the enrollment log sheet (*Appendix vii*) with the participant's assigned study ID and treatment arm.
- The study ID only will also be written on her clinical case-notes (source document).

2. Go to REDCap

- Complete participant's biodata and locator form (Appendix viii): For each participant, the research nurse (RN) will obtain contact information, which will include the participant's phone number, her partner's phone number, her home address, major landmark to her home, occupation, and other necessary information as provided by the participant. The RN should determine the best way to collect this information for each study participant and complete it in the participant's biodata and locator form. If a participant misses a scheduled appointment (follow-up or end of study visit), the research staff will try to establish communication with the participant through authorized possible means (e.g., phone, emails or visiting the participant's home or workplace). The need to complete all scheduled follow up visits must be emphasized to all study participants at enrolment and at every visit.
- Take relevant medical history and concomitant medication information.
- Do a physical examination
- Evaluate for the presence of any symptom and sign (adverse event(s) AEs)) and if any,
 complete and submit the adverse event e-form (Appendix ix).
- **Complete enrollment e-CRF (***Appendix x***)** and relevant source document (SD) to document relevant baseline observation.
- Take blood samples for laboratory tests complete the blood sample collection log.
- Administer study drug (intervention or control) according to randomization and protocol for study drug administration (section 4.6.1)

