7 ADVERSE EVENTS AND REPORTING REQUIREMENTS

7.1 Adverse Events

- An adverse event (AE) is the appearance or worsening of any undesirable sign, symptom, or medical condition occurring after starting the study drug even if the event is not considered to be related to study drug. Study drugs include the investigational drug/ control drug under evaluation that is given during the treatment phase of the study.
- Medical conditions/diseases present before starting study drug are only considered adverse events if they worsen after starting study drug.
- Abnormal laboratory values or test results constitute adverse events only if they induce clinical signs or symptoms, or are considered clinically significant, or require therapy. E.g., hypophosphatemia requiring treatment.
- Clinical signs and symptoms will be assessed at baseline, before dosing and at all follow-up visits, and recorded in the e-CRF. Any symptom that worsens or starts after baseline will be recorded as a new adverse event on the e-CRF.
- The occurrence of adverse events, such as fever, weakness, chills/rigors, headache, myalgia, dizziness, epigastric pain, abdominal pain, anorexia, nausea, vomiting, diarrhea, palpitations, insomnia, pruritus, coughing, tinnitus, abnormal gait, tremor, clonus, or dyskinesia, will be sought by the investigator (or designee) at each study visit and recorded in the e-CRF.
- Adverse events also may be detected when they are volunteered by the patient during or between visits or through physical examination, laboratory test, or other assessments.

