9.3 Data Management and analysis

The assignment of participants into analysis populations will be performed prior to database lock and any data analysis.

- Randomized all participant who receive a randomization number.
- Intention-to-treat (ITT) all randomized patients with at least one relevant post-baseline efficacy assessment, and who had at least one dose of study drug. Following the intention-to-treat principle, patients will be analyzed according to the treatment they were assigned to at randomization.
- Primary Analysis (PA) all ITT patients that completed 2- and 6-weeks postpartum visit.
- Per Protocol (PP) all PP patients that meet all the following:
 - Took at least 80% of scheduled study drug
- Safety all patients that received at least one dose of study drug and had at least one post-baseline safety assessment. Patients will be analyzed according to treatment received.

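### Section 4.10.2 randomizes the woman and logs her arm before the baseline symptom check against which later adverse events are judged, and provides no blinded assessor for it

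*Protocol*

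**What the plan says.** Protocol 4.10.2 numbers the steps that follow screening and consent.

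- Step 1 is randomization: "Go to Sealed Envelope and randomize the participant into a study arm". The study ID is created here, and the enrollment log is completed "with the participant's assigned study ID and treatment arm". Only the study ID goes on the case notes.
- Step 2 moves to REDCap. After the contact details the list runs: "Take relevant medical history and concomitant medication information"; a physical examination; "Evaluate for the presence of any symptom and sign (adverse event(s) AEs)) and if any", an adverse event form is submitted; the enrollment e-CRF; "Take blood samples for laboratory tests complete the blood sample collection log"; and last, "Administer study drug (intervention or control) according to randomization and protocol for study drug administration".

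Section 7.1 gives the baseline its role in the safety analysis: "Any symptom that worsens or starts after baseline will be recorded as a new adverse event on the e-CRF". It asks for the symptom assessment before dosing but does not say before randomization.

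Section 4.5 lists the adverse event form among the subjective instruments whose data collector is to be blinded to allocation. Section 4.4 has the site research nurses or midwives screen, consent, enrol and randomize. Section 4.1 gives each site two research nurses.

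**The concern.** A baseline that serves as the reference for an outcome is best fixed before anyone can know the allocation. Here the arm is on paper at the site before anyone asks about symptoms. Many of the symptoms listed in 7.1, such as weakness, headache, dizziness, nausea and abdominal pain, depend on how closely the woman is questioned and how readily she reports them. If baseline questioning is more thorough in one arm, more of her existing complaints are on record there, and fewer later complaints count as new. The other arm then appears to have more adverse events for reasons unrelated to the drug.

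Adverse drug events are part of objective (b) in 2.2 and are secondary outcome (q) in 3.1.2. The document also promises a safeguard in 4.5 that 4.10.2 does not deliver.

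**Working it through.** The plan states no figure on this point. The check is a comparison of sections.

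**1. Order as written.** Eligibility and point-of-care hemoglobin (4.10.1), consent (4.10.1), randomization with the arm logged (4.10.2 step 1), then history and co-medication, examination, symptom check with adverse event form, enrollment e-CRF, blood samples and study drug (4.10.2 step 2). The step 2 items are instructions to take, do, evaluate and administer, and they end in dosing. This is a sequence of procedures, not only of data entry. No other section puts the baseline symptom check before randomization. Section 4.7 reinforces the order, because the study ID that identifies the forms is generated only when the woman is randomized.

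**2. What depends on the baseline.** Under 7.1 a symptom is a new event if it starts or worsens after baseline, and a pre-existing condition counts only if it worsens. Under 7.2 an event reported at enrollment before dosing is classed as unrelated to study drug. What is written down at this visit therefore affects both the count and the attribution of later events.

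**3. Whether blinding is carried through.** Section 4.5 promises a blinded collector for the adverse event form. At the 2-, 6- and 12-week visits (4.10.3) and at end of study (4.10.5), the visit e-CRF opens only after the adverse event form and any scales due have been submitted. That keeps compliance data, which would reveal the arm, until after the subjective forms. Section 4.10.2 uses the same adverse event form but has no such gate, and does not say that someone other than the randomizing nurse completes it. Sections 4.5 and 4.10.2 are not reconciled.

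**4. How a recording difference would act.** Let *b* be the proportion of women with a given symptom before dosing, *r* the probability that it is recorded at baseline, and *q* the probability that an unrecorded one is later reported and entered as new. The spurious new-event proportion in an arm is *b*(1 − *r*)*q*. If *b* and *q* are equal across arms, the spurious difference (intravenous minus oral) is *bq*(*r*_oral − *r*_IV). Two things follow. The sign depends on which arm is questioned more fully, and the document does not settle that. The shift is also smaller than the recording difference itself, because it is multiplied by *b* and *q*. The document gives none of *b*, *r* and *q*, so no size can be computed.

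**5. What is not exposed.** Entry hemoglobin, all eligibility criteria and the history needed for the exclusions are settled in 4.10.1, before allocation. Blood samples are drawn before dosing and, apart from point-of-care tests, are analyzed by an outside laboratory (4.9). The exposure is limited to history, examination and symptoms.

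**The case against.** The strongest reply is that the protocol already provides for blinding. Section 4.5 names the adverse event form, each site has two research nurses so that one can randomize while the other assesses, and the case notes carry only the study ID. Nothing says that the randomizing nurse fills in the baseline form, or when the woman learns her arm. This stands in part. It cannot be asserted that nurse and woman do know the arm at that point, only that the enrollment steps allow it and nothing in them prevents it.

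A second reply is that onset dates (7.2.4) and a relatedness scale that uses timing (7.2.3) help to identify symptoms that predate the drug. They help, but an onset date recalled at a later visit does not replace a baseline record.

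A third reply is that women know their treatment throughout follow-up, so open-label reporting remains whatever the order at enrollment. That is true. Reordering removes one source of bias, not all of them.

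Two stronger readings should be resisted. A reader might infer that the step order causes arm-related losses from the primary analysis, because 9.3 limits the intention-to-treat set to women "who had at least one dose of study drug". Those losses would come from that definition and from refusal on learning the arm in an open-label trial. Eligibility is already settled, and the recheck of hypersensitivity risk before each infusion (7.3.1.1) follows allocation in any order. No length of delay is given either. A reader might also want a false-positive rate for the adverse event comparison. That would need an assumed event incidence and an assumed recording difference carried one-for-one into incidence, and the document supports neither.

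**Conclusion.** The point holds in a limited form. Section 4.10.2 places allocation, with the arm logged, before the subjective baseline assessments. Section 7.1 makes those assessments the reference for new adverse events, and the blinding described in 4.5 is not built into the enrollment steps. The comparison of symptomatic adverse events could be biased in either direction by an amount the document does not allow one to estimate.

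The primary outcome, sample size, entry hemoglobin, eligibility and laboratory outcomes, including hypophosphatemia, are not materially affected. The conclusion assumes that sites follow the steps in the listed order and that no procedure outside the protocol separates the two nurses' roles at enrollment. It is a modest weakness in a stated objective, worth correcting because the correction is cheap.

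**What to change.** Reorder 4.10.2. After consent, complete medical history, co-medication, examination and the baseline symptom and adverse event form under a screening-log number, and lock them in REDCap. Only then call Sealed Envelope, generate the study ID and link it to the screening number. Add a gate like the one in 4.10.3 and 4.10.5, so that randomization is not called until the baseline forms are submitted. The wording of 7.1 should say that baseline symptoms are assessed before randomization as well as before dosing, which also brings 4.10.2 into line with 4.5.

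The blood draw can stay where it is, after randomization under the study ID and before dosing. Laboratory results are little exposed to knowledge of the arm, and this avoids temporary labels on tubes sent from 20 sites to an outside laboratory, with the mismatch risk they would bring.

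The cost is a changed step order, a number in the screening log if it does not already carry one, and one ID-linking step.
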